8.8. Biomarkers

Unless prohibited by local regulations or IRB/EC decision, the following samples for biomarker research are required and will be collected from all participants in this study as specified in the [SoA](#):

- Pre-treatment tumor tissue samples to enable assessment of PD-L1 status and cluster of differentiation 8 (CD8) + TIL, whole exome sequencing and gene expression analyses
- 4 mL whole blood samples at baseline and on treatment to enable immune repertoire analyses, epigenetic profiling and filtering of somatic mutation data
- Two 10 mL blood samples at baseline and on treatment to be processed to plasma to enable assessment of cfDNA
- Approximately one 10 mL blood sample at baseline and on treatment to be processed to serum to facilitate proteomic profiling

The objectives of biomarker analyses applied to pre-treatment (TURBT), on-treatment and end-of-treatment tumor biospecimen are to evaluate candidate predictive biomarkers that may be proven useful in identifying participants who may preferentially benefit from the

study treatments and to evaluate mechanisms of action and/or resistance for each of the combinations being assessed.

As of 12 September 2022, no biomarker samples will be collected from participants enrolled in Cohorts B1 and B2.

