9.4.3.5. Biomarkers

In Cohort A, biomarker data will be assessed separately for tumor tissue and peripheral blood. Summary statistics for levels of PD-L1 expression, and number and percentage of participants with tumors categorized with baseline PD-L1 expression level (high vs low) will be presented by arm for Cohort A and overall. For exploratory biomarkers, summary statistics for pre-treatment biomarkers will be presented and summary statistics for on-treatment biomarkers will additionally include the ratio to baseline for continuous biomarkers, and a contingency table for non-continuous biomarkers, as appropriate.

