**Table 2. Study Objectives and Endpoints (Cohort A)**

Objectives	Endpoints
	abnormalities as characterized by type, severity (as graded by NCI CTCAE v5.0), and timing

 
• To assess the effects of PF-06801591+BCG (induction and maintenance or induction) and BCG (induction and maintenance) on patient-reported health-related quality of life in participants with high-risk NMIBC.
 
	
 
• Health-related quality of life as measured by: 1) EORTC QLQ-C30 (European Organization for Treatment of Cancer Quality of Life Questionnaire), 2) EORTC QLQ-NMIBC24, 3) PTAB (Patient Treatment Administration Burden Questionnaire)
 

 
• To characterize the PK of PF-06801591+BCG (induction and maintenance or induction).
 
	
 
• <math>C_{trough}</math> of PF-06801591 when in combination with BCG (induction and maintenance or induction); Arms A and B only.
 

 
• To evaluate the immunogenicity of PF-06801591+BCG (induction and maintenance or induction).
 
	
 
• ADAs; Nabs of PF-06801591 when in combination with BCG (induction and maintenance or induction); Arms A and B only.
 

 
• To evaluate PD-L1 expression in pre-treatment tumor tissue that may aid in the identification of a participant subpopulation most likely to benefit from treatment with PF-06801591 + BCG (induction and maintenance or induction).
 
	
 
• Tumor sample biomarker status based on PD-L1 expression (high or low)
 

Tertiary/Exploratory	

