**Table 5. Biomarker Definition and Determination**

Parameter	Definition	Method of Determination
PD-L1 expression	The number of PD-L1 positive cells and/or qualitative assessment of PD-L1 staining on tumor and immune cells in regions of interest that are defined by tumor cell morphology.	Pathologist, assisted by image analysis

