### **5.1.2. Decision rules (Cohort A only)**

Prior to protocol amendment 5, two interim (IA1(futility only) and IA2) and final (FA) analyses were planned for the primary endpoint of Cohort A.

IA1 for EFS was conducted after 658 participants were randomized to Cohort A for all 3 arms combined. As IA1 was for futility only, no alpha was spent at IA1.

Based on protocol amendment 5, the IA2 will be removed, and the FA for EFS based on a calendar-based data cut-off date will be conducted. Randomization to Cohort A was completed on 16 November 2021 and the EFS FA data cut-off date will be set to allow for approximately 3 years of follow-up after last randomized participant.

Cohort A of the study will be considered positive if the primary objective is met.

One interim and one final efficacy analyses are planned for OS endpoints. The IA for OS will be performed at the time of the final analysis for EFS. The FA for OS will be performed at the end of the study, which is approximately 5 years after the last participant has been randomized in Cohort A:

- IA: at the time of the final analysis for EFS; approximately 64 OS events (64% of the 100 OS events expected for each comparison) are expected to have occurred for each comparison.
- FA: this will occur at the end of the study, approximately 5 years after last participant randomized; approximately 100 OS events are expected to have occurred for each comparison.

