### **Exploratory analyses to investigate the impact of potential prognostic or effect modifying (predictive) factors**

See subgroups as defined in [Section 6.4](#).

Multivariable Cox's regression analysis will be carried out to assess and adjust the treatment effect for relevant baseline factors of potential prognostic impact. A stepwise selection procedure will serve to identify explanatory variables of potential prognostic values additional to the randomization strata which will be included in all models during the selection procedure. The Cox's Proportional Hazard model is defined as:

$$h(t) = h(0;t) e^{Xb}$$

where  $h(0;t)$  defines the baseline hazard function and  $X$  defines the vector of explanatory variables and  $b$  the unknown vector of regression parameters.

In the stepwise selection procedure, variables are entered into and removed from the model in such a way that each forward selection step can be followed by one or more backward elimination steps. The stepwise selection process terminates if no further variable can be added to the model or if the variable just entered into the model is the only variable removed in the subsequent backward elimination. The level of significance for an explanatory variable to enter the model is set to 0.15 (p-value of Score test) and the significance level for removing it is set to 0.40 (p-value of Wald test). This analysis will be performed using the stepwise selection method in SAS (Proc PHREG). Once this procedure stops, the factor "treatment arm" will be added to the last selected model in order to evaluate the effect of treatment on EFS time when adjusted for the selected explanatory variables. The hazard ratios of all selected explanatory variables and of treatment effects will be reported including 2-sided 95% CIs. No interactions will be considered. Post-baseline factors will not be considered for the model.

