#### **6.2.5. Biomarker endpoints**

Summary statistics for levels of PD-L1 expression, and number and percentage of participants with tumors categorized with baseline PD-L1 expression level (high vs low) will be presented by arm for Cohort A.

Biomarker data, if available, for Cohort B1 and/or Cohort B2 will be provided in a listing only.

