### **6.4. Subset Analyses (Cohort A only)**

Subset analyses, if applicable, will be performed for OS, EFS, and CR per investigator assessment as noted below, based on the FAS for the subgroups defined below.

The following subgroups will be defined and used for analyses:

- Randomization stratification factor(s)
  - Presence of CIS per IRT (EFS per investigator, and OS)
    - Yes (Reference)
    - No
  - Geography
    - US (Reference)
    - Western Europe and Canada
    - ROW
- Presence of CIS per CRF (EFS per investigator and OS only)
  - Yes (Reference)
  - No
- Age
  - Age < 65 years (Reference)
  - Age  $\geq$  65 years
- Sex
  - Male (Reference)
  - Female

- Race
  - White (Reference)
  - Asian
  - Black or African American
  - Other
- Ethnicity
  - Hispanic or Latino or of Spanish origin
  - Not Hispanic or Latino or of Spanish origin (Reference)
- TICE Strain
  - TICE (Reference)
  - No TICE
- BCG strain at induction
  - TICE (Reference)
  - RIVM
  - TOKYO172
  - BCG-1
  - CHINA D2PB302
- T1 disease at baseline per CRF (EFS per investigator and OS only)
  - Yes
  - No (Reference)

Subset analyses for EFS and OS will use the censoring rules described in Sections 6.1.1.1, Section 6.2.2.1 and Section 6.2.2.2.

Treatment arms will be compared for each endpoint using a 2-sided unstratified log-rank test for each subgroup level and the unstratified HR and its corresponding 95% CI will be computed per subgroup level.

Subset analyses for difference in CR rates will be performed and the 2-sided 95% CI will be provided.

All the subset analyses will be unstratified and exploratory; no adjustment for multiplicity will be performed. In the case of a low number of participants within a category (<5% of the FAS) and low number of events within the category (< 10 events) the categories will be pooled or in cases where no meaningful pooling can be performed, the category may not be summarized.

To assess the heterogeneity of treatment effects for EFS and OS across the subgroup levels, a Cox's regression models will be fitted with EFS and OS as the dependent variable,

respectively, and subgroup, treatment, and the treatment-by-subgroup interaction as explanatory variables.

- Model: treatment + subgroup + treatment×subgroup-variable

A p-value for the interaction test (Wald's test) will be provided together with the HR and corresponding 95% CI for the interaction model parameter.

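### The only planned PD-L1 output is expression and high/low status by arm, so the part of the secondary objective about who benefits gets no analysis; PD-L1 is missing from the SAP 6.4 subgroups and no high/low cut-off is stated

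*SAP*

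**What the plan says.** The objective. SAP Table 2 (and Protocol 3.1) lists a Cohort A secondary objective to evaluate PD-L1 in pre-treatment tumor tissue "that may aid in the identification of a participant subpopulation most likely to benefit from treatment". The paired endpoint is PD-L1 status, high or low. Protocol 8.8 gives the purpose of tumor biomarker work as "to evaluate candidate predictive biomarkers that may be proven useful in identifying participants who may preferentially benefit".

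The analysis. SAP 6.2.5 plans "Summary statistics for levels of PD-L1 expression, and number and percentage of participants with tumors categorized with baseline PD-L1 expression level (high vs low"), by arm. Protocol 9.4.3.5 likewise starts from "Summary statistics for levels of PD-L1 expression" and plans the same summary by arm and overall.

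The definition. SAP Table 5 defines PD-L1 expression as "The number of PD-L1 positive cells and/or qualitative assessment of PD-L1 staining on tumor and immune cells in regions of interest", read by a pathologist with help from image analysis. It gives no threshold.

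The subgroups. SAP 6.4 opens its list with "The following subgroups will be defined and used for analyses" and then names ten factors: CIS per IRT, geography, CIS per CRF, age, sex, race, ethnicity, TICE strain, BCG strain at induction, and T1 disease per CRF.

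**The concern.** Saying who benefits requires an outcome compared between arms at each PD-L1 level. Counts of high and low status by arm in a randomized cohort show baseline balance and nothing more. If the plan is followed exactly, that part of the objective produces no result.

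PD-L1 is not incidental to this trial. The rationale cites retrospective evidence linking higher expression to BCG failure, and tissue for PD-L1 testing is required by inclusion criterion 4. Yet ethnicity and two BCG-strain splits receive interaction tests, while the marker whose own objective refers to benefit does not.

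The practical risk is a late addition. The trial is open-label, and SAP 7.1 keeps by-arm aggregate data from the study team only until the snapshot for the primary analysis. If a PD-L1 subgroup is requested after that, nothing in these two documents fixes either the analysis or the cut-off.

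**Working it through.** **Step 1: does any other section supply the analysis?**

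| Place | What it provides | Treatment effect by PD-L1? |
|---|---|---|
| SAP 6.2.5; Protocol 9.4.3.5 | Levels and high/low counts | No |
| SAP 6.4 | Subgroup HRs and interaction models (EFS, OS), CR-rate differences, forest plots, for ten listed factors | No; PD-L1 is not listed |
| SAP 6.2.2.3, multivariable Cox model (same method for OS in 6.2.2.4) | Refers back to the 6.4 factors; "No interactions will be considered" | No |
| SAP 6.3.2 | Descriptive summaries of exploratory biomarkers | No |
| SAP 6.2.4 | Optional modelling of drug exposure | No |

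Protocol 9.4.3 leaves exploratory biomarker analyses to the SAP, and the SAP does not include this one.

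**Step 2: is high versus low defined?** Table 5 allows positive-cell counts, qualitative staining, or both, on tumor and immune cells, and gives no scoring rule or cut-off. By contrast, SAP Table 24 gives numeric cut-offs for the immunogenicity assays (ADA titer 99, nAb titer 4).

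**Step 3: reproduce the plan's own power figure.** SAP 5.1.1 states 68.7% power for 174 EFS events, HR 0.69, 1-sided 0.025. With 1:1 allocation, power = Φ(√174 × |ln 0.69| / 2 − 1.960) = Φ(2.447 − 1.960) = 68.7%, which agrees. At 1-sided 0.023 the result is 67.4%, also as stated. The documents give no figure for a PD-L1 analysis.

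**Step 4: precision of a PD-L1 interaction for EFS and OS.** Inputs from the documents, per two-arm comparison: 174 EFS events (SAP 5.1.1); for OS, "approximately 64 OS events (64% of the 100 OS events expected for each comparison") at the interim (SAP 5.1.2), so 64 at the interim and 100 at the final analysis. Assumptions, because the documents give neither: the share p of events in PD-L1-high participants (50%, 30% or 20%), and an evaluable result for every event except in the second row.

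SE of the log ratio of HRs = √(4/(D·p) + 4/(D·(1−p))), where D is the number of events. The 95% CI is the estimate multiplied or divided by exp(1.96 × SE). For D = 174 and p = 0.5: SE = √(4/87 + 4/87) = 0.303, and the factor is 1.81.

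| Events D | p = 0.5 | p = 0.3 | p = 0.2 |
|---|---|---|---|
| EFS, 174 | 1.81 | 1.91 | 2.10 |
| EFS, 139 (80% of 174 evaluable) | 1.94 | 2.07 | 2.30 |
| OS interim, 64 | 2.66 | 2.91 | 3.40 |
| OS final, 100 | 2.19 | 2.35 | 2.66 |

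Power for a true EFS ratio of HRs of 0.7, 174 events, 2-sided 0.05: with δ = |ln 0.7| / SE, power = Φ(δ − 1.96) + Φ(−δ − 1.96). This gives 22%, 19% and 16% for p = 0.5, 0.3 and 0.2.

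**Step 5: precision for CR.** The planned minimum of 250 participants with CIS gives about 83 per arm. Assume the same CR rate r in both arms, between 50% and 80%. The half-width of the 95% CI for the difference in rates is 1.96 × √(2r(1−r)/n), with n = (250/3) × the subgroup's share.

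| Subgroup share | n per arm | r = 0.8 | r = 0.5 |
|---|---|---|---|
| 50% | 41.7 | ±17.2 points | ±21.5 points |
| 20% | 16.7 | ±27.2 points | ±33.9 points |

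**The case against.** The objective can be read more narrowly. Its verb is to evaluate expression, the reference to benefit is a hedged subordinate clause, and the paired endpoint is status alone, which SAP 6.2.5 delivers. The sentence in Protocol 8.8 covers all tumor biomarkers, not PD-L1 in particular. This stands as far as it goes: no named endpoint is left without output. The gap is between the purpose given for the objective and the analysis planned for it.

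A cut-off may be recorded in a laboratory or assay document that was not supplied, and the high/low table cannot be produced without one. That also stands, so the finding is only that the protocol and SAP do not state it. A citation would be enough.

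At 16% to 22% power, a PD-L1 subgroup can neither establish nor exclude that PD-L1 identifies who benefits. True, but SAP 6.4 already treats all its subgroups as exploratory, without multiplicity adjustment and with a pooling rule for sparse categories. Low precision is a reason for that label, not for leaving out the one factor tied to a secondary objective.

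The objective could instead be reworded as descriptive. That would make the documents consistent, but it drops the question rather than answering it.

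Time may be short. SAP version 8 is dated 10 December 2024, and the EFS cut-off is planned about three years after 16 November 2021. The documents do not show when the snapshot is taken.

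**Conclusion.** The concern holds. The plan reports PD-L1 status by arm and contains no analysis of treatment effect by PD-L1, so the benefit part of the secondary objective has no output. Neither document states the high/low cut-off.

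The consequence is limited: the primary and key secondary conclusions and the type I error rate are untouched. A listed PD-L1 subgroup would describe rather than confirm, and it would be weakest for OS and CR. The precision figures depend on assumed PD-L1 shares, evaluability and CR rates, and the CR figures also on the planned minimum of 250, since the actual number with CIS is not given. That the analysis is missing depends on none of these.

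**What to change.** - In SAP 6.4, add baseline PD-L1 (high, low), with missing or not evaluable results reported separately. For EFS and OS, use the existing subgroup HR, interaction model and forest plot; for CR, the difference in rates and its forest plot. Label the analysis exploratory.
- In SAP Table 5, state the PD-L1 scoring method and high/low cut-off, or cite the document that does. Fix them before by-arm aggregate data are seen.
- If aggregate data have already been seen, label the analysis post hoc.

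The cost is one subgroup entry, one sentence or reference, a count of non-evaluable results and one more row per forest plot. No new sampling is needed, because tissue is already an entry requirement, although the documents do not show how many results are evaluable. The drawback is one more low-precision exploratory subgroup.

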#### **6.2.6. Endpoints for immunogenicity data of PF-06801591**

All analyses described below will be performed on ADA and nAb data from participants who received PF-06801591. Data will be summarized by treatment in Cohort A (Arm A and Arm B) and combined across both treatment arms, unless otherwise specified.

Blood samples for PF-06801591 immunogenicity testing will be collected pre-dose ( $\leq 0$  hr actual time) of the PF-06801591 injection on Day 1 relative to PF-06801591 dosing of Cycles 1, 2, 4, 6, 8, 10, 13 and EOT of Cohort A

Samples positive for ADA will be analyzed for titer and may be analyzed for nAb.

Participants will be characterized into different ADA and nAb categories based on the criteria defined in Table 24.

**Table 24. Participants Characterized Based on Anti-Drug Antibody Results (ADA Status) and Neutralizing Antibody Results (nAb Status)**

Term	Definition
ADA-positive sample	ADA sample titer $\geq 99$
ADA-negative sample	ADA sample titer $< 99$
nAb-positive sample	nAb sample titer $\geq 4$
nAb-negative sample	nAb sample titer $< 4$
Pre-existing ADA/nAb	Positive ADA/nAb at baseline (e.g. day 1 pre-dose)
Cross-reactivity	This often refers to immunogenicity testing against an endogenous antigen, biosimilar reference product or another biotherapeutic within the same therapeutic class.
Subject-level immunogenicity analysis population	
ADA evaluable population	All subjects with $\geq 1$ post-treatment ADA result.
nAb evaluable population	ADA-positive subjects with $\geq 1$ post-treatment nAb result, plus all ADA-negative subjects. An ADA-positive subject without any post-treatment nAb data is excluded from the analysis population.
Subject-level definitions	
Treatment-induced ADA	Baseline ADA titer is missing or negative and subject has $\geq 1$ post-treatment positive ADA titer.
Treatment-boosted ADA	Baseline ADA titer is positive and subject has a $\geq 4$ -fold dilution increase in ADA titer from baseline in $\geq 1$ post-treatment sample.
ADA-positive subject	A subject with $\geq 1$ treatment-induced or treatment-boosted ADA response.
ADA-negative subject	An ADA evaluable subject without treatment-induced or treatment-boosted ADA response. Subject either has (1) all ADA-negative results throughout the study or (2) is ADA positive at baseline but did not become treatment-boosted post dose.
ADA incidence	The percent of ADA-positive subjects in a treatment group/cohort or study.
Treatment-induced nAb	Baseline nAb titer is missing or negative or ADA-negative and subject has $\geq 1$ post-treatment positive nAb titer.
Treatment-boosted nAb	Baseline nAb titer is positive and subject has a $\geq 4$ -fold dilution increase in nAb titer from baseline in $\geq 1$ post-treatment sample.
nAb-positive subject	An ADA-positive subject with $\geq 1$ treatment-induced or treatment-boosted nAb response. For ADA-positive (treatment-boosted) subjects, subject is nAb positive only if the subject has $\geq 1$ treatment-induced or treatment-boosted nAb response at the visit where the subject has a treatment-boosted ADA response. For visits where the subject did not show a boosted ADA response, the subject is classified as nAb-negative for the visit even if the subject has post-treatment positive nAb titer for that visit.
nAb-negative subject	nAb evaluable participant who is either (1) an ADA-negative subject or (2) an ADA-positive subject without treatment-induced or treatment-boosted nAb response (i.e. subject has all nAb-negative results throughout the study or subject is nAb positive at baseline but did not become treatment-boosted post dose). Note: in the event a subject is ADA-positive at baseline but did not show a boosted response post-treatment, subject is classified as ADA-negative and nAb-negative at the subject level even if the subject has post-treatment positive nAb titer, as all such ADA-negative subjects are nAb-negative regardless of nAb titer data.
nAb incidence	The percent of nAb-positive subjects in a treatment group/cohort or study.
Duration of ADA and nAb response (subject-level definitions):	
Transient ADA	An ADA-positive subject with (1) a treatment-induced or treatment-boosted ADA sample detected only at 1 sampling time (excluding the last time point) post-treatment, or (2) treatment-induced or treatment-boosted ADA samples detected at $\geq 2$ time points where the first and last positive samples (irrespective of any negative samples in between) are separated by $< 16$ weeks, and the subject's last sample is ADA negative.
Persistent ADA	An ADA-positive subject with first and last positive ADA samples (treatment-induced or treatment-boosted) detected over a period of $\geq 16$ weeks post-treatment, irrespective of any negative samples in between.

**Table 24. Participants Characterized Based on Anti-Drug Antibody Results (ADA Status) and Neutralizing Antibody Results (nAb Status)**

Term	Definition
Indeterminate ADA	An ADA-positive subject who is not persistent or transient.
Transient nAb	A nAb-positive subject with (1) a treatment-induced or treatment-boosted nAb sample detected only at 1 sampling time (excluding the last time point) post-treatment, or (2) treatment-induced or treatment-boosted nAb samples detected at $\geq 2$ time points where the first and last positive samples (irrespective of any negative samples in between) are separated by $< 16$ weeks, and the subject's last sample is nAb negative or ADA negative.
Persistent nAb	A nAb-positive subject with first and last positive nAb samples (treatment-induced or treatment-boosted) detected over a period of $\geq 16$ weeks post-treatment, irrespective of any negative samples in between.
Indeterminate nAb	A nAb-positive subject who is not persistent or transient.

Note: Duration of response (persistent, transient or indeterminate) definitions are only applicable to ADA (or nAb)-positive subjects.

All ADA and nAb data will be listed, and the number and percentage of participants in each ADA and nAb category will be summarized by treatment arm for Cohort A and combined across treatment arms. Incidence of ADA and nAb positive participants and time to first ADA and nAb detection will also be summarized by treatment arm for Cohort A and combined across treatment arms. Incidence may also be presented graphically and, if  $\geq 10\%$  in a treatment arm, immunogenicity titer data will also be summarized and box plots of PK concentrations by ADA and nAb status will be presented.

Where data are summarized by visit, results will be summarized as windowed visit (i.e., cumulatively from the day/time of prior visit to the day/time of current visit) to allow inclusion of results from unplanned visits. Data from samples collected at EOT will be presented in individual listings and will be included in categorical assessments and summaries.

Immunogenicity data available for Cohort B1 and/or Cohort B2 will be provided in listings only.

